### **13.2. Clinical Assessments After Study Drug Discontinuation**

Subjects who have not received study drug will not be followed up on leaving the study.

For subjects who have received study drug and who prematurely discontinue from the study treatment (ie, do not complete all visits through Follow-up), every effort should be made to complete the final evaluation procedures, in accordance with the early termination (ET) visit described in [Section 11.9.4](#).

## **14. STUDY TERMINATION**

The Sponsor reserves the right to discontinue the study at this study center for safety or administrative reasons at any time while safeguarding that early termination does not compromise subjects' safety or well-being. In particular, a study center that does not recruit at an acceptable rate may be closed. Should the study be terminated, and/or the study center closed for whatever reason, all documentation and study medications pertaining to the study must be returned to the Sponsor or its representative.

If, in the opinion of the Investigator, clinical observations suggest it may be unsafe to continue, the Investigator may terminate part or the entire study after consultation with the Sponsor.

In the event of study or site termination, subjects will be required to undergo final evaluation procedures, in accordance with the early termination (ET) visit described in [Section 11.9.4](#).

## 15. STATISTICS

### 15.1. Sample Size

This study is designed to determine the magnitude of a possible pharmacological effect of SEP-363856 on dopamine synthesis capacity. Dopamine synthesis capacity has shown good test-retest reliability ([Egerton-2010](#)). Prior studies have reported a within-subject standard deviation of 0.00056/min in dopamine synthesis capacity. The absolute elevation in dopamine synthesis capacity for schizophrenia cases versus normal healthy controls is estimated to be approximately 0.001/min, and to have a correlation of approximately 0.6 with symptoms. Given this relationship between dopamine synthesis capacity and symptoms, it is estimated that a decrease in dopamine synthesis capacity of 0.0005/min in patients is the smallest reduction likely to be clinically significant (anticipated to translate into > 20% reduction in symptoms which is generally considered the smallest change readily detected in clinical practice). A sample size of 16 subjects treated with SEP-363856 will provide > 90% power to detect a treatment reduction of 0.0005/min (change from baseline) in dopamine synthesis capacity using a paired sample t-test and alpha set at the 0.05 level.

Subjects who are initiated on treatment but discontinue from the study may not be replaced. The total sample size will be 22 subjects to allow for up to 25% drop-out to obtain complete PET scans on at least 16 subjects.

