#### **Statistical Methods:**

**PET Analysis:** The region of interest in the primary endpoint is the whole striatum. Exploratory analyses will be conducted in other regions and sub-regions of interest. The cerebellum will be used

as the reference region. Dopamine synthesis capacity will be calculated based on each individual PET images collected at each scan for each subject.

**Statistical Analysis:** The analysis of brain dopamine synthesis capacity and fMRI analysis will use the PET population, which include subjects who were administered at least one dose of SEP-363856 and have a baseline and a post-baseline PET assessment. The change from baseline in dopamine synthesis capacity at Week 2 will be calculated, together with 95% confidence interval from a paired sample t distribution. Changes in resting state BOLD fMRI signal at each post-dose time point from baseline will be summarized. Changes in exploratory MRI markers, including (but not limited to) neuromelanin and iron signal at each post-dose time point from baseline will be summarized. The efficacy population will include all subjects who have received at least one dose of SEP-363856, and have any postdose data for the PANSS, CGI-S, BNSS or MADRS. Efficacy data will be based on this population. Changes from baseline at each post-dose time point will be summarized, with 95% confidence intervals.

Safety analyses will use the Safety population, which includes all subjects who have received at least one dose of study drug. Safety measures will be summarized descriptively.

Treatment emergent adverse events (TEAEs) will be summarized by presenting the number and percentage of subjects with any TEAEs, and AEs by system organ class and preferred term. Adverse events will be further summarized by severity and by relationship to study drug. The summary of TEAEs will be limited to events occurring on or after the first dose of study drug. All AEs, as well as a listing of deaths, SAEs, or AEs leading to discontinuation, will be presented in listings.

Vital signs, ECG parameters, and laboratory data will be summarized by presenting summary statistics of actual values and change from baseline values. The number and percentage of subjects with potentially clinically significant post-baseline values for selected parameters will be presented. The incidence of orthostatic hypotension and orthostatic tachycardia will be summarized.

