## 7.3. Rationale

### 7.3.1. Rationale for the Study Design

This is an open-label, flexibly-dosed, study evaluating the effect on brain dopamine synthesis capacity as measured by F-DOPA PET imaging of adjunctive open-label administration with SEP-363856 (50 to 75 mg/day) over 2 weeks in adults with schizophrenia. The 2-weeks of treatment will provide an adequate timeframe within which to evaluate the effects of SEP-363856 in this subject population.

Patients with schizophrenia and other psychotic disorders show altered presynaptic dopaminergic function, as supported by the use of PET-imaging techniques ([Jauhar-2017](#)). The radiotracer F-DOPA has been commonly used to measure dopamine turnover in PET studies and has consistently reported elevated  $K_i$  values in patients with schizophrenia with a summary effect size of 0.8 on meta-analysis, and effect sizes of 1.1 - 1.3 with the current high-resolution PET scanners. Several lines of evidence suggest that increased presynaptic dopamine synthesis capacity and greater baseline dopamine dysfunction are associated with responsiveness to D2-based antipsychotic treatments ([Howes-2014](#)). On the other hand, it has been hypothesized that treatment resistance may be linked to a different underlying neurobiology which is more glutamatergic and less dopaminergic. This is supported by the finding that pre-synaptic

dopamine synthesis capacity has been shown to be reduced in treatment resistant schizophrenia ([Demjaha-2012](#), [Kim-2017](#)). Given that up to 30% of the schizophrenic population is treatment-resistant, this is an area of significant unmet need, and treatments focused on alternative targets to the D2 receptor are therefore of great interest.

Trace Amine-Associated Receptor 1 (TAAR1) agonists have come to light in recent years as potential targets for the treatment of schizophrenia and related psychotic disorders. With the development of highly selective ligands, there is evidence to suggest that TAAR1 agonists may act as negative modulators of dopaminergic signaling within the mesolimbic system where they are predominantly expressed ([Rutigliano-2018](#)). On the basis of PET imaging experiments in animal models, Study SEP361-118 is designed to investigate the effect of SEP-363856 administration adjunctive to an antipsychotic on striatal dopamine synthesis capacity, as measured using F-DOPA PET imaging.

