### 6. ANALYSIS POPULATIONS

Enrolled subjects are subjects who signed the ICF and did not screen fail at their final screening.

Three analysis populations will be defined in this study. The population for PET and fMRI analyses will be specified in a separate Statistical Analysis Plan.

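### Does calling 0.00056/min a within-subject SD undermine the claim of more than 90% power with 16 subjects?

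*Protocol*

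**What the plan says.** Protocol Section 15.1 and the Sample Size paragraph of the synopsis give the same justification. After noting that "Dopamine synthesis capacity has shown good test-retest reliability", with a citation to a test-retest study of the tracer, they state: "Prior studies have reported a within-subject standard deviation of 0.00056/min in dopamine synthesis capacity". That sentence has no citation of its own. With 16 treated subjects, power is put above 90% "to detect a treatment reduction of 0.0005/min (change from baseline) in dopamine synthesis capacity", using a paired t-test at alpha 0.05. Sidedness is not stated there. The total is set at 22 so that a loss of up to a quarter still leaves 16 subjects with both scans.

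The stated purpose is estimation: "This study is designed to determine the magnitude of a possible pharmacological effect of SEP-363856 on dopamine synthesis capacity". The primary analysis (synopsis, Statistical Methods; Section 15.3.6) reports the change at Week 2 "together with 95% confidence interval from a paired sample t distribution".

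The supplied SAP has no sample-size section. It leaves imaging to another document: "The population for PET and fMRI analyses will be specified in a separate Statistical Analysis Plan". That document was not available for this review.

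**The concern.** The paired t-test works on one difference per subject, so its power depends on the SD of those differences. Neither passage names that SD, gives a correlation between scans, or shows a conversion. Taken strictly, a within-subject SD is the spread of repeated single measurements in one person. The difference of two such measurements has √2 times that SD. On that reading the stated power fails by a wide margin, and the only justification offered for 16 evaluable and 22 enrolled subjects falls with it. The placement of the figure, straight after a sentence on test-retest reliability, makes the strict reading natural. The stake is whether the trial is adequately sized to detect the smallest fall that the protocol regards as clinically meaningful.

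**Working it through.** **Inputs (Protocol Section 15.1, repeated in the synopsis).** Difference δ = 0.0005/min; SD 0.00056/min; n = 16; alpha 0.05; loss 25%; total 22. I take alpha as two-sided, in line with the 95% confidence interval in Section 15.3.6, and give one-sided values as well.

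**Formula.** Exact power of a paired t-test: noncentral t with n − 1 degrees of freedom and noncentrality λ = (δ / SD of change) × √n, compared with the critical value of the central t.

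**Reading A: 0.00056/min is the SD of the change.**
- δ / SD = 0.0005 / 0.00056 = 0.893; at n = 16, λ = 0.893 × 4 = 3.57.
- Two-sided power: 89.5% at n = 15, 91.5% at n = 16, 97.9% at n = 22.
- Enrolment: 16 / (1 − 0.25) = 21.3, rounded up to 22.

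The stated power, the 16 and the 22 all reproduce, and 16 is the first n to reach 90%.

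**Reading B: 0.00056/min is a per-scan SD.**
- SD of change = √2 × 0.00056 = 0.00079/min.
- δ / SD = 0.631; at n = 16, λ = 0.631 × 4 = 2.53.
- Two-sided power: 65.6% at n = 16, 80.6% if all 22 have paired scans. Reaching 90% would take 29 pairs.

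| | Reading A | Reading B |
|---|---|---|
| SD of change (/min) | 0.00056 | 0.00079 |
| Power, n = 16, two-sided | 91.5% | 65.6% |
| Power, n = 16, one-sided | 96.1% | 77.8% |
| Power, n = 22, two-sided | 97.9% | 80.6% |
| Half-width of 95% CI at n = 16 (/min) | 0.00030 | 0.00042 |

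The half-width is t(0.975, 15) × SD / √16, with the planning SD put in for the observed one. A one-sided test does not bring Reading B to 90% at 16. Under Reading A a one-sided test would reach 90% at n = 13, so the exact fit at 16 depends on a two-sided alpha.

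**Margin under Reading A.** The largest SD of change that keeps 90% at n = 16 is 0.000576/min, and 0.000576 / 0.00056 = 1.029, a margin of 2.9%.

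**A weak cross-check on reliability.** Section 15.1 puts the elevation in patients at about 0.001/min, and Section 7.3.1 reports "a summary effect size of 0.8 on meta-analysis, and effect sizes of 1.1 - 1.3 with the current high-resolution PET scanners". Assume that these share one between-subject SD, which the documents do not say. That SD is then 0.001 divided by the effect size, and reliability is 1 − (per-scan error variance / total variance). The error variance is 0.00056²/2 under A and 0.00056² under B.
- Effect size 1.1: total variance (0.001/1.1)²; reliability 0.81 (A) or 0.62 (B).
- Effect size 1.3: 0.74 (A) or 0.47 (B).
- Effect size 0.8: 0.90 (A) or 0.80 (B).

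This leans towards A at the higher effect sizes. At 0.8 both readings are compatible with good reliability, so I give it little weight.

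**The case for a change.** The best case for a change is that a sample-size statement should be reproducible from its own words, and this one is not if its label is taken in the standard sense. The gap between 91.5% and 65.6% is large. Even the favourable reading has almost no slack, since an SD of change only 2.9% higher takes power below 90%. In a study meant to size an effect, an interval half-width of 0.00042 rather than 0.00030/min matters against a target of 0.0005/min. Subjects also receive radiation on the strength of this justification. A source check and a few reworded words would settle the matter.

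Some of this stands. The label is ambiguous, the figure has no citation of its own, and the margin is thin. But the term is also used loosely for the SD of within-subject change. The same paragraph names both the paired test and the change from baseline, so that reading is open to any statistician who reworks the sum. The thin margin follows from choosing the smallest n that reaches 90%; it is not an error. The 66% figure applies only under the less likely reading, and nothing in the documents favours that reading beyond the wording of the label.

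Nor is the rewording free: Protocol Section 17.5 requires sponsor, ethics committee and HRA approval even for a non-substantial amendment. Under the likelier reading, that effort would leave the number of subjects, the power and the analysis as they are.

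**Conclusion.** The concern does not call for a change. The arithmetic holds when 0.00056/min is taken as the SD of the paired change: two-sided power is 91.5% at 16, with 16 the smallest n reaching 90% and 22 following from 25% loss. That agreement makes a loosely labelled SD of differences the most plausible explanation. It is an inference, and it rests on a two-sided alpha of 0.05.

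The documents cannot exclude the per-scan reading, because the source of the figure is not among them. If that source showed a per-scan SD, the planning claim would be overstated, with power of about 66% at 16 and about 81% with all 22. The documents do not show this, so underpowering is not established.

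The results do not depend on the answer. The primary estimate and its interval are computed from the observed SD of the change, and the reported interval will show the precision achieved. What remains is a point of terminology that a careful reader can resolve from the test, the sample size and the total.

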### 15.2. Analysis Populations

The following populations will be defined:

- Safety Population: The safety population will consist of all subjects who receive at least one dose of study drug.
- PET Population: The PET population is defined as all subjects who took at least one dose of SEP-363856 and have a baseline and a post-baseline PET assessment.
- Efficacy population: the efficacy population is defined as all subjects who have received at least one dose of study drug, and have any postdose data for the PANSS, CGI-S, BNSS or MADRS.
- Per Protocol Population: The Per Protocol Population is defined as all subjects in the PET population, the subject completed the study, and the subject had NO important protocol deviations.

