j Blood samples for antipsychotic plasma concentrations will be collected at Screening, Day -2, Day 1 (approximately 10 minutes prior to dosing), Day 2 (2 - 4 hours postdose), Day 7 (2 – 4 hours postdose), Day 14 (prior to PET scan), and at Follow-up.

k Additional urine drug screen may be ordered as deemed clinically appropriate. These results should be discussed with the Medical Monitor.

l Each PET scan will be accompanied by intravenous administration of radiotracer  $^{18}\text{F}$ -DOPA and oral pre-treatment (1 hour prior to tracer) with 150 mg carbidopa and 400 mg entacapone. If PET/MR scanner is unavailable for technical reasons separate PET and MR scans (on an alternate PET scanner without MR and alternate MR scanner) will be permitted. Prior to each PET scan, there is a period of resting state fMRI collection. In addition to fMRI scan sequences, exploratory MRI sequences may be performed during each of the MRI and PET/MR acquisition times and may include (but not limited to) a neuromelanin-sensitive MRI (NM-MRI) sequence and an iron-sensitive MRI sequence (effective transverse relaxation rate [R2\*] or Quantitative Susceptibility Mapping [QSM]). Repeat MRI including exploratory MRI sequences may be performed where it is not possible to obtain complete measures during the PET-MRI scan.

m In the event of unsuccessful PET scan on Day 14, additional days of dosing may be necessary up to, but not exceeding, Day 19. If any such additional days are necessary, subjects will continue their usual daily dosing. PANSS, BNSS, MADRS, and CGI-S may be assessed  $\pm 1$  day of PET scan; other assessments are to be completed the same day as the PET scan. Participants will only receive 3 PET scans in the event that a scan is not able to be completed or is not suitable for analysis. It is expected that the majority of participants will receive up to 2 PET scans which would result in an effective dose of 7.4 mSv.

n PET scan to be performed at early termination (ET) visit only if the subject terminates the study prior to Day 14 PET scan.

o Only perform PANSS, BNSS, CGI-S, and MADRS if subject discontinues prior to Day 14 scan day.

p At the screening visit, the “Baseline/Screening” version will be completed; the “Since Last Visit” version of the C-SSRS will be administered for all other visits. C-SSRS should be performed prior to PET scan on Day 14.

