## 6. STUDY ENDPOINTS

### 6.1. Primary Endpoint

Change from baseline in dopamine synthesis capacity at Week 2 using F-DOPA.

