#### **10.3.1. Prohibited Medications**

Concomitant use of CYP2D6 inhibitors is prohibited as SEP-363856 is a potential substrate for CYP2D6.

All psychotropic medications and herbal supplements (with the exception of the single, background antipsychotic, or medications listed in [Section 10.3.4](#)) are prohibited during the study and must be discontinued, as tolerated and clinically appropriate (for at least 5 half-lives or 14 days, whichever is longer), prior to the first dose of study drug in a manner that is consistent with labeling recommendations and conventional medical practice.

Clozapine is prohibited. Prior exposure to clozapine is allowed, as long as treatment is discontinued at least 120 days prior to PET scan at screening.

Subjects who require treatment with one or more of the prohibited concomitant medications (including antidepressants, mood stabilizers, or anxiolytics [lorazepam or equivalent at doses above protocol-specified limits]) will be discontinued (as appropriate) from the study.

All efforts will be made to complete the PET and resting state fMRI scans intended by the protocol even in cases of discontinuations of study drug or procedures.

The majority of participants will receive up to 2 PET scans. Participants will only receive 3 PET scans in the event that a scan is not able to be completed or is not suitable for analysis.

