#### **11.9.4. Early Termination (ET)**

The following procedures will be at this visit:

- Collect concomitant medications.
- Physical examination
- Vital sign measurements
- Weight
- Perform ECG.
- Collect blood sample for clinical laboratory evaluation (hematology, chemistry, serum prolactin, and fasted glucose panel and lipid panel).
- Collect blood sample for determination of plasma SEP-363856 and SEP-363854 concentration.
- Collect blood sample for antipsychotic levels.
- Female subjects only, collect urine samples for pregnancy test (any positive test must be followed up with a serum  $\beta$ -hCG test).
- Collect urine sample for urine drug screen (UDS).
- Perform psychiatric assessments in the following order: PANSS, BNSS, MADRS, C-SSRS, CGI-S. (Only perform PANSS, BNSS, MADRS, CGI-S if early termination occurs prior to Day 14 PET/MR scan.)
- BARS
- AIMS
- SAS
- Collect adverse events
- Perform PET/MR Scan including fMRI (only perform if the subject terminates the study prior to the Day 14 PET/MR Scan).

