### **15.3.6. Positron Emission Tomography (PET) and Functional Magnetic Resonance Imaging (fMRI) Analysis**

The analysis of brain dopamine synthesis capacity and fMRI analysis will use the PET population.

The region of interest in the primary endpoint is the whole striatum. Exploratory analyses will be conducted in other regions and sub-regions of interest. The cerebellum will be used as the reference region. The regions of interest will be delineated on the subjects structural MR based on using the Hammersmith Atlas, and this will be co-registered to the subject's dynamic PET images. Dopamine synthesis capacity will be calculated based on each individual PET images collected at each scan for each subject using a Patlak Graphical Analysis. For the fMRI image pre-processing will be performed via the CONN toolbox (version 17.b)(65) for Statistical Parametric Mapping software (SPM 12 (6906)). For each participant, BOLD signal time-series will be extracted from the nodes in the Gordon cortical atlas, and functional connectivity determined within primary networks of interest (the default mode network, the salience network) and the visual network (a control network), and additional networks guided by the PET analysis.

The primary endpoint is the change from baseline in dopamine synthesis capacity at Week 2 will be calculated, together with 95% confidence interval from a paired sample t distribution.

Changes in resting state BOLD fMRI signal within the salience, default mode, and visual networks at each post-dose time point from baseline will be summarized.

Changes in exploratory MRI markers, including (but not limited to) neuromelanin and iron signal at each post-dose time point from baseline will be summarized.

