### **17.3. Informed Consent**

The informed consent form will be approved by the Sponsor/CRO prior to submission to the IRB/IEC. The Sponsor/CRO may provide a template informed consent form to be qualified by each research facility to conform to local requirements. All informed consent forms must contain the minimum elements as mandated by ICH GCP, applicable local law(s) and regulations and will be subject to Sponsor/CRO approval as well as IRB/IEC approval. The Sponsor/CRO may submit informed consent forms to a central IRB/IEC for review and approval or favorable opinion contingent upon prior Investigator permission and review.

Before recruitment and enrollment, each prospective subject will be given a full explanation of the study, allowed to read the approved informed consent form and be provided ample time and the opportunity to ask any questions that may arise. Once all questions have been answered and the Investigator is assured that the prospective subject understands the implications of participating in the study, the prospective subject will be asked to give consent to participate in the study by signing the informed consent form. As part of the consent process, each prospective subject must consent to direct access to his/her medical records for study-related monitoring, auditing, IRB/IEC review, and regulatory inspection. It should be clearly explained to each prospective subject that participation in each and every clinical visit and assessment is expected. The subject may be discontinued from study medication, but that does not necessarily negate the expectation that the subject will continue to participate in the study through the final visit/assessment. The Investigator will provide a copy of the signed informed consent form to each subject and will record the date of the informed consent on the CRF.

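### Could PET scans made at early termination, or after study drug was stopped, dilute the primary Week 2 change?

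*Protocol*

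**What the plan says.** Protocol 15.2 defines the PET population as all subjects who "took at least one dose of SEP-363856 and have a baseline and a post-baseline PET assessment". Protocol 15.3.6 states: "The analysis of brain dopamine synthesis capacity and fMRI analysis will use the PET population". The primary endpoint in Protocol 6.1 is "Change from baseline in dopamine synthesis capacity at Week 2".

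Several places produce, or might produce, scans made off drug:

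- Table 2, footnote n: "PET scan to be performed at early termination (ET) visit only if the subject terminates the study prior to Day 14 PET scan". Protocol 11.9.4 repeats the condition ("only perform if the subject terminates the study prior to the Day 14 PET/MR Scan"). Its list of procedures contains no study-drug dose, whereas the Day 14 list in 11.9.2.6 does.
- Protocol 10.3.1 asks for all efforts to "complete the PET and resting state fMRI scans intended by the protocol even in cases of discontinuations of study drug or procedures".
- Protocol 17.3 says that a subject "may be discontinued from study medication, but that does not necessarily negate the expectation that the subject will continue to participate in the study".

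Protocol 13.2 points the other way. For dosed subjects who stop treatment early, "every effort should be made to complete the final evaluation procedures, in accordance with the early termination (ET) visit".

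The SAP's early-termination (ET) rules do not reach PET. SAP 7.3 moves ET data to the next planned time point for efficacy, safety and PK data, and SAP 15.2 lets an ET assessment stand in for Day 14 on the clinical rating scales. SAP 5.3 excludes PET and fMRI analysis, SAP 6 leaves the imaging population to a separate plan, and SAP 4.2 drops the Per Protocol population for imaging as well as safety.

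**The concern.** Protocol 15.1 gives the aim as the magnitude of a pharmacological effect. Protocol 7.1 and 11.4 place the post-dose scan about 2 to 4 hours after the Day 14 dose, near peak plasma concentration. A scan made some days after the last dose measures something else, yet the population definition admits it.

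There are two routes. A subject who leaves before Day 14 is scanned at the ET visit, with no limit on time since the last dose. Or a subject stops study drug, stays in the trial and is scanned on Day 14, which makes the scan nominally a Week 2 value. If either kind of scan were counted and the effect had worn off, the estimated on-drug change would shrink and its 95% confidence interval would cover the on-drug effect less often than stated. The one protocol-defined set that required study completion is no longer to be formed.

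**Working it through.** **The plan's own figures.** Inputs from Protocol 15.1: reduction 0.0005/min, SD 0.00056/min, paired t-test, alpha 0.05 (taken as two-sided), 16 evaluable subjects, 25% drop-out.

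- Standardised effect: 0.0005 / 0.00056 = 0.893. Noncentrality: 0.893 × √16 = 3.57 on 15 df. Exact power is 0.915, which agrees with the stated figure of over 90%.
- Enrolment: 16 / (1 − 0.25) = 21.3, rounded up to 22, as stated.
- Read as a per-scan SD, 0.00056 gives an SD of change of 0.00056 × √2 = 0.00079 and power of only 0.656. The plan's figure is reproduced only if 0.00056 is the SD of the change.

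**Dilution if off-drug scans were counted.** Let k be the number of off-drug scans among n pairs and r the share of the effect that they retain. Then

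relative dilution = k(1 − r)/n, and expected reduction = 0.0005 × [1 − k(1 − r)/n].

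The documents give neither k nor r. As a ceiling for k, 0.25 × 22 = 5.5, so at most 5 drop-outs. Power and coverage of the on-drug effect come from simulation (400,000 trials per cell, two-sided 5% t-test on the change, SD 0.00056), with n = 22:

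| k | r | Dilution | Expected reduction (/min) | Power | Coverage |
|---|---|---|---|---|---|
| any | 1 | 0% | 0.000500 | 0.979 | 0.950 |
| 1 | 0 | 1/22 = 4.5% | 0.000477 | 0.964 | 0.950 |
| 2 | 0 | 2/22 = 9.1% | 0.000455 | 0.945 | 0.943 |
| 3 | 0 | 3/22 = 13.6% | 0.000432 | 0.917 | 0.929 |
| 5 | 0 | 5/22 = 22.7% | 0.000386 | 0.836 | 0.880 |
| 3 | 0.5 | 1.5/22 = 6.8% | 0.000466 | 0.958 | 0.944 |
| 5 | 0.5 | 2.5/22 = 11.4% | 0.000443 | 0.939 | 0.931 |

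If five subjects drop out and only some are scanned, 17 on-drug pairs remain. Alone they give power 0.932. Adding one, two or three off-drug scans with r = 0 gives dilution of 1/18 = 5.6%, 2/19 = 10.5% or 3/20 = 15%, and power 0.913, 0.896 or 0.875. With r = 0.5, power stays at about 0.93.

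Under the per-scan reading of the SD, five off-drug scans of 22 with r = 0 give power 0.560 against 0.806 undiluted, and coverage 0.913.

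**Whether the plan counts such scans.** The provisions side by side:

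1. Membership of the PET population is not the same as having a value for the endpoint. The endpoint is tied to Week 2, and Table 2 gives Week 2 and ET separate columns.
2. Protocol 15.3.11 imputes nothing. A subject with only an ET scan therefore has no Week 2 value unless a rule supplies one.
3. The SAP writes such rules for the data that it covers (7.3 and 15.2). Neither supplied document has one for PET.
4. Protocol 15.1 enrols 22 so that at least 16 have complete scans after drop-out. Drop-outs are thus planned as not contributing.
5. An off-drug Day 14 scan is unlikely. The footnote to Figure 1 keeps subjects in clinic and on treatment until the Visit 2 scans are done, Protocol 7.1 puts a dose a few hours before the scan, and 13.2 sends those who stop treatment to the ET procedures.

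**The case for a change.** The strongest contrary point is the trial's own convention. For every kind of data that the SAP covers, ET results are carried to the next visit, so an imaging analyst could follow suit and treat an ET scan as Week 2. The population wording would allow it. Because the aim is to estimate a magnitude, bias and coverage matter more than power, and in the r = 0 scenario above, three off-drug scans added to 17 on-drug pairs lower power despite the larger n.

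It stands that neither supplied document says outright how an ET or off-drug PET scan is treated. It does not stand that this makes a stated rule wrong. The SAP's conventions expressly leave PET out, and the plan that governs PET was not supplied. The under-coverage is measured against the on-drug effect only. If the target is the effect in everyone dosed and scanned, those scans belong in the mean. An on-drug primary set would instead select subjects who tolerated treatment to Day 14. Reasonable statisticians would differ on which should lead.

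Dropping the Per Protocol population adds little, since the protocol assigned no analysis to it.

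**Conclusion.** No change to the plan follows. What remains is a missing detail: the handling of ET and off-drug PET scans is not written in the protocol or the supplied SAP, and the separate imaging SAP is where it would be expected. Until then, the Week 2 endpoint, the separate ET visit and the absence of imputation point to leaving ET scans out of the primary mean. Analysts can identify any such scan from the recorded scan times (Protocol 11.4), the dosing listing (15.3.2) and the plasma sample taken at the ET visit (11.9.4).

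The bias is possible, not shown. It needs three things together: off-drug scans occur, they are counted as Week 2, and they retain less than the full effect. Under the plan's effect and SD, one to three such scans among 22 pairs with nothing retained mean dilution of 4.5% to 13.6%, power of 0.92 or more and coverage of 0.93 or more. The 23% dilution, with power 0.84 and coverage 0.88, requires every permitted drop-out to be scanned, all other pairs to be usable and no effect to persist. These figures are illustrations, because neither k nor r can be taken from the documents. The choice between an on-drug set and all dosed and scanned subjects is a fair trade-off, not an error.
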